Up to 45 patients with SCA of different types will undergo a non-invasive stimulation plus gait and postural control training. The total duration of sessions will last 30 minutes during which participants will simultaneously receive 20 min of trans-spinal tDCS and perform a gait training protocol with progressively greater difficulties, previously tested in patients with SCA. The trans-spinal tDCS will be applied at an intensity of 2mA, with the anodic electrode positioned over the cerebellar region and the cathodic electrode over the thoracic region of the spinal cord (approximately vertebra T11). The intervention will be applied over four consecutive weeks on weekdays except weekends, totaling 20 sessions.

All participants will receive real stimulation, so there will be no control group. Given that it may be difficult to recruit additional SCA individuals willing to participate in a control group or to find patients with similar characteristics who do not receive treatment during the study period, also due to the progressively debilitating condition of the participants (SCA) and given their socio-economic conditions that limit their transportation, it would be ethically questionable to deprive a group of patients of receiving a potentially beneficial treatment, especially when there is no established standard therapy or other effective treatment options available to them.

The equipment to be used for stimulation will be an NKL Stimulator. The continuous current offered will be supplied through a pair of 5x7 cm (35 cm²) electrodes wrapped in sponges moistened with saline solution. The anode electrode will be positioned over the cerebellar region. To do this, the inion region will be located. Using a measuring tape, the point 2cm above the inion will be identified and the electrode will be fixed to the scalp, using appropriate adjustable bands. The cathode electrode will be positioned over the spinal region, more precisely, at the level of T8. To precisely find this position, the thoracic spinous processes will be palpated, and the 11th process located. Using a measuring tape, identify the point located 2 cm below T11 and fix the electrode with adhesive tape at this point. The stimulation intensity will be 2mA.

Initially, participants will be evaluated (ASSESSMENT 1) through the application of the SARA scale; modified dynamic gait index (mDGI); The Berg Balance Scale; Timed up and go (TUG); Inventory of non-ataxic signs (INAS);

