The four-stage test; Ten-meter walk test with an accelerometer; and perform other three tasks using an accelerometer of a mobile phone: (i) 5 times sit-to-stand; (ii) Functional Reach Test; and (iii) a test consisted in move arms and head standing with foot together. Three physiotherapist experts in these evaluations who will not participate in the intervention sessions will conduct this part. Then, 20 successive tDCS sessions will be applied to the participants. Every 5 tDCS sessions, the mDGI and TUG assessment will be reassessed (ASSESSMENT 2, 3, and 4). At the end of the 20 sessions, all instruments will be reapplied except for INAS (ASSESSMENT 5). A month after the end of the intervention the individuals will be reassessed except for the tests using the accelerometer (ASSESSMENT 6).

Before and after each session, individuals will be evaluated using the one-leg stand test proposed in the miniBestest instrument. In this test, the individual must remain standing, with their eyes open and fixed on a point 1.6 to 3m away with their hands on their waist. The participant must remove a lower limb from the support, without assistance, flexing it backward and remaining there. The time spent in the position will be measured in seconds, from the moment the evaluator says "now" until the elevated foot touches the ground again, or the upper limbs move from the initial position. The test will be repeated twice for each lower limb. Both times will be noted, and the highest time will be considered.

At the end of 20 sessions, individuals who complete the intervention will be also interviewed with a semi-structurally questionnaire by a researcher who did not take part in the study. The method that will be used to analyze the interviews will be the framework approach, which consists of a deductive form of analysis that starts from pre-defined research objectives. The framework approach is a systematic method that allows for in-depth analysis, in which the researcher extracts codes from the interviewees' statements, forms categories, and finally acquires refined themes useful for describing the participants' ideas and perceptions. All interviews will be conducted face-to-face. The interviews will be recorded for future transcription, using a smartphone. Once the interviews have been transcribed, the content will be analyzed using ATLAS.ti® software, and, finally, the themes that most faithfully represent the concepts found in the interviews will be chosen.

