Inclusion Criteria:

1. Individuals aged 18 to 70, without distinction of gender or ethnicity;
2. Diagnosed with spinocerebellar ataxia, of any type, by a neurologist;
3. With mild to moderate ataxia severity;
4. Able to walk 2 meters even when using a walker, cane or crutch;
5. Score ≥ 21 (BERTOLUCCI et al., 1994) on the Mini-Mental State Examination (MMSE; FOLSTEINet al., 1975; ALMEIDA, 1998);
6. No other concomitant neurological changes.

Exclusion Criteria:

1. Illiterate;
2. Being subjected to any other experimental physiotherapeutic or medicinal intervention during the clinical trial;
3. Skin condition that may affect the electrode placement site
4. Musculoskeletal, neurological or cardiorespiratory disorders that prevent the tests from being carried out;
5. Epilepsy;
6. Pregnancy;
7. History of brain surgery;
8. History of seizures;
9. Metallic implants in the skull that interfere with neuromodulation;

Outcome Measures**Primary Outcome Measure:****1. Postural control**

The Berg Balance Scale (BBS) measures functional balance and fall risk in 14 tasks. Each item is given a score of 0-4, with a total score between 0 and 56, being the higher the score, the better the individual's performance. The Berg scale also predicts the risk of falls. A score equal to or less than 45 points indicates a greater risk of falls.

The four-stage test (4-stage) assesses static balance and measures an individual's ability to hold a series of four balance positions, each more challenging than the previous, for at least 10 seconds each.

[Time Frame: (i) Baseline, (ii) after 20 sessions and (iii) in follow up (one month).]

2.Mobility

Timed up and go (TUG) assesses mobility, balance, walking ability and the risk of falling. On the command "go", the patient gets up from the chair, walks 3 meters, turns around, returns to the chair, and sits down. The time is calculated in seconds. The longer the time taken, the greater the risk of falling

[Time Frame: (ii) Baseline, (ii) at the end of sessions 5, 10, 15 and 20 (each session is 1 day) and (iii) in follow up (one month)]

3.Gait performance

Measured by the Modified Dynamic Gait Index (mDGI) which total score is from 0 (severe gait impairment) to 64 (no gait impairment) and a Ten-meter walk test with an accelerometer fixed at the sacrum to assess step and stride time, speed, and gait cadence.

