[Time Frame: (ii) Baseline, (ii) at the end of sessions 5, 10, 15 and 20 (each session is 1 day) and (iii) in follow up (one month)]

4.Accelerometry

To perform three tasks using an accelerometer of a mobile phone fixed on the participant's waist: (i) 5 times sit-to-stand; (ii) Functional Reach Test; and (iii) a test consisted in move arms and head standing with foot together. The accelerometer will register how the body is moving and changing speed over time while performing tasks.

[Time Frame: (i) Baseline and (ii) after 20 sessions.]

Secondary Outcome Measures:

The subjective experience of the participants regarding the protocol.

Semi-structured interview regarding subjective experience of the participants relative to the study intervention

[Time Frame: At the end of session 20 (each session is 1 day)]

The presence of non ataxic signals (INAS) and the disease severity (SARA)

INAS is an inventory to detect the presence or absence of 16 non-ataxic signs and symptoms through a clinical physical examination. SARA is an instrument to

evaluate the disease severity through eight tasks including gait, balance, speech and coordination that produce a total score of 0 (no signs of ataxia) and 40 (more severe ataxia).

[Time Frame: (i) Baseline and (ii) after 20 sessions.]

References

ALMEIDA, OP Mini mental state examination and the diagnosis of dementia in Brazil. Archives of Neuro-Psychiatry, v. 56, n. 3B, p. 605–612, Sept. 1998.

BARRETO, TL. et al. Transcranial direct current stimulation in the treatment of cerebellar ataxia: A two-phase, double-blind, auto-matched, pilot study. Clin Neurol Neurosurg. 2019 Jul; 182:123-129. doi: 10.1016/j.clineuro.2019.05.009. Epub 2019 May 14. PMID: 31121471.

BENUSSI, A. et al. Long-term clinical and neurophysiological effects of cerebellar transcranial direct current stimulation in patients with neurodegenerative ataxia. Brain Stimulation. 2017 Mar-Apr;10(2):242-250. doi: 10.1016/j.brs.2016.11.001. Epub 2016 Nov 3. PMID: 27838276.

BENUSSI, A. et al. A randomized, double-blind, sham-controlled, crossover trial. Neurology. 2018 Sep 18;91(12): e1090-e1101. doi: 10.1212/WNL.0000000000006210. Epub 2018 Aug 22. PMID: 30135258.

BENUSSI, A. et al. Therapeutic Potential of Non-Invasive and Invasive Cerebellar Stimulation Techniques in Hereditary Ataxias. Cells. 2023 Apr 20;12(8):1193. doi: 10.3390/cells12081193

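### The outcome time frames and the visit schedule disagree on the ten-metre walk, INAS and SARA; the walk's declared one-month value appears not to be collected

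*Protocol*

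**What the plan says.** Section 3, Design and Methods, sets out six assessments.

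- Assessment 1 is the full battery: "Initially, participants will be evaluated (ASSESSMENT 1) through the application of the SARA scale; modified dynamic gait index (mDGI); The Berg Balance Scale", then TUG, INAS and the four-stage test, and finally "Ten-meter walk test with an accelerometer; and perform other three tasks using an accelerometer of a mobile phone".
- Assessments 2 to 4 are short: "Every 5 tDCS sessions, the mDGI and TUG assessment will be reassessed (ASSESSMENT 2, 3, and 4").
- Assessment 5: "At the end of the 20 sessions, all instruments will be reapplied except for INAS (ASSESSMENT 5").
- Assessment 6: "A month after the end of the intervention the individuals will be reassessed except for the tests using the accelerometer (ASSESSMENT 6").

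The Outcome Measures section attaches a time frame to each outcome heading. Primary outcome 3, gait performance, consists of the mDGI and a "Ten-meter walk test with an accelerometer fixed at the sacrum to assess step and stride time, speed, and gait cadence". Its single time frame is baseline, then "at the end of sessions 5, 10, 15 and 20 (each session is 1 day) and (iii) in follow up (one month"). Primary outcome 4, accelerometry, consists of the three phone tasks and is timed at baseline and after 20 sessions only. The secondary outcome "The presence of non ataxic signals (INAS) and the disease severity (SARA") has one joint time frame, also baseline and after 20 sessions.

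**The concern.** Anyone running the visits follows section 3; anyone analysing the trial follows the outcome list. For three instruments these lead to different data sets.

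The serious case is the ten-metre walk at one month. Whether benefit is retained at one month is part of main question (i) in the Abstract and is aim (iv) in section 2, and gait parameters are part of the trial's main goal. Step time, stride time, speed and cadence enter the primary outcomes only through this walk. If the follow-up visit omits it, retention of those parameters cannot be tested, although the outcome list declares that time point. No statistical analysis plan can supply a measurement that was never taken.

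**Working it through.** There is no stated figure to reproduce. The check sets each instrument's declared times against the assessments that deliver them. Assessments 1 to 6 correspond to baseline, sessions 5, 10, 15 and 20, and one month.

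| Instrument | Declared times | Scheduled at | Mismatch |
|---|---|---|---|
| BBS, four-stage test | baseline, 20, one month | 1, 5, 6 | none |
| TUG | baseline, 5, 10, 15, 20, one month | 1 to 6 | none |
| mDGI | baseline, 5, 10, 15, 20, one month | 1 to 6 | none |
| Ten-metre walk | baseline, 5, 10, 15, 20, one month | 1, 5; 6 in doubt | 5, 10, 15 absent; one month absent or in doubt |
| Three phone tasks | baseline, 20 | 1, 5 | none |
| SARA | baseline, 20 | 1, 5, 6 | one month undeclared |
| INAS | baseline, 20 | 1; 6 if taken literally | 20 absent; one month unclear |

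**The walk at one month.** The exclusion at assessment 6 can be read in three ways.

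- Reading A: every accelerometer test is dropped, including the walk. The baseline list supports this. It describes the walk as done with an accelerometer and then introduces the phone tasks as the other three that use one. One-month parameters: 0 of 4.
- Reading B: only the three phone tasks of primary outcome 4 are dropped. One-month parameters: 4 of 4.
- Reading C: only the sensor is dropped and the walk is timed by hand. Speed is then distance over time, so 1 of 4. This is an assumption, because the protocol lists speed among the accelerometer measures and mentions no separate timing.

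**Size against the whole set.** Instruments under primary headings that declare one month: BBS, four-stage test, TUG, mDGI and the walk, so 5. The first four need no accelerometer. Therefore 4 of 5 are secure and 1 of 5 depends on the reading.

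**Count of mismatches, instrument by instrument.** Under reading A: walk 4 (sessions 5, 10, 15, one month) + INAS 2 (session 20 absent, one month extra if assessment 6 is taken literally) + SARA 1 (one month extra) = 7. Of these, 4 + 1 = 5 are declared values with no measurement scheduled. Under reading B the walk contributes 3, giving 3 + 2 + 1 = 6, of which 3 + 1 = 4 are declared but unscheduled.

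**If time frames apply to a heading as a whole.** The mDGI then covers 6 of 6 declared times for outcome 3, and SARA covers session 20 for the joint INAS and SARA outcome, so both conflicts become loose wording. The extra one-month time for SARA remains: 3 scheduled times (baseline, session 20, one month) − 2 declared = 1 undeclared.

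**The case against.** The strongest reply is that reading B reconciles the two sections at one month. Primary outcome 4 is itself headed accelerometry, contains only the phone tasks and has no one-month time, which is just what an exclusion of accelerometer tests would produce. The walk sits under gait performance, which does declare one month. This is a real argument and the reason for saying that the walk appears to be omitted. It does not settle the matter, because the baseline list counts the walk among the accelerometer tests. Even under reading B the walk is not scheduled at sessions 5, 10 and 15.

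A second reply is that time frames belong to headings, not instruments. The protocol does not say so. Under outcome 1, which also groups two instruments, the shared time frame fits each of them.

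A third is that the firmest contradictions (INAS after session 20, the walk at the interim sessions) are the least important, while the important one depends on interpretation. That is fair as description. The interim walk values matter little because no aim calls for them and mDGI and TUG follow the course between visits. INAS enters aim (i) as a predictor, for which baseline suffices. SARA at one month is an extra value, not a lost one, and it rests on assessment 6 naming only what is left out.

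It also stands that no aim names the walk explicitly and that mDGI still measures gait at one month. This limits the damage to the four walk parameters; it does not remove the conflict over a declared primary-outcome value.

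**Conclusion.** The concern holds. The schedule and the outcome list disagree on three instruments, and the text does not say which governs. The consequence that matters is the walk at one month: 0, 1 or 4 of its 4 parameters would be available, depending on how one sentence is read, and the natural reading gives 0.

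This rests on two assumptions: that a time frame applies to every instrument under its heading, and that the assessment 6 exclusion covers the walk. That the wording conflicts is certain; that the one-month walk is lost is probable.

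The limits are clear. Retention remains testable on BBS, the four-stage test, TUG and mDGI, and the walk's change from baseline to session 20 is unaffected. The INAS, SARA and interim-walk discrepancies are minor. The point should be fixed because a missed follow-up value cannot be recovered and the correction is cheap.

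**What to change.** Replace the shared time frames with one instrument-by-visit table covering assessments 1 to 6, and use it in both section 3 and Outcome Measures.

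- **Ten-metre walk:** give it its own time frame, separate from the mDGI. Either keep it, with the sensor, at the one-month visit, as outcome 3 now declares, or state in outcome 3 that it is not done then and confine retention claims to BBS, the four-stage test, TUG and mDGI.
- **INAS:** list it as a baseline predictor only, or remove its exclusion at assessment 5.
- **Assessment 6:** name the instruments applied, rather than only those left out. State whether SARA and INAS are among them, and align their time frame.

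The cost is wording. Keeping the walk adds one short sensor test at a visit that already takes place.

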NCT06267222

**Trans-spinal Electrical Stimulation in
Individuals with Spinocerebellar Ataxia**

October, 2023

Abstract

The main goal of this pragmatic clinical trial is to investigate the effects of trans-spinal tDCS in individuals with spinocerebellar ataxia (SCA) over some parameters of gait and postural control in real-world conditions, reflecting daily clinical practice. The main questions it aims to answer are: (i) If an extended number of tDCS sessions, beyond the typical 5 to 10 sessions described in scientific literature, applied concomitantly with exercises with progressive challenges, to yield positive outcomes over some parameters of gait and postural control in individuals with SCA and if there is retention of possible benefits one month later the end of this protocol; (ii) If there is specific characteristics (including balance, gait, mobility, severity of ataxia, DNA test characteristics and non-ataxic signs) in individuals with SCA that can predict their improvement in postural control and gait following the 20 tDCS sessions. Participants will receive 20 tDCS sessions concomitantly with exercises for gait and postural control with progressive challenges. Postural control and gait of the participants will be assessed in two big sessions before (#assessment 1) and after the 20 sessions (#assessment 5) and 3 small sessions after every 5 sessions (#assessments 2, 3 and 4). Also, as a follow-up, they will be assessed a month after the end of the intervention (#assessment 6).

1. Scientific background

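### Read literally, TUG and mDGI are tested after a session during treatment but session-free at baseline and follow-up, so two of the main contrasts may include a single-session effect

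*Protocol*

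**What the plan says.** The time frames are in the Protocol under Outcome Measures. For primary outcomes 2 (Mobility, TUG) and 3 (Gait performance, including mDGI) the wording is the same: baseline, then "at the end of sessions 5, 10, 15 and 20 (each session is 1 day"), then follow-up at one month.

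Section 3, Design and Methods, is less specific. Baseline (Assessment 1) comes first: "Then, 20 successive tDCS sessions will be applied to the participants". For the interim visits it says "Every 5 tDCS sessions, the mDGI and TUG assessment will be reassessed (ASSESSMENT 2, 3, and 4"), and for the last on-treatment visit "At the end of the 20 sessions, all instruments will be reapplied except for INAS (ASSESSMENT 5"). The Abstract calls the interim visits "3 small sessions after every 5 sessions (#assessments 2, 3 and 4"). Follow-up (Assessment 6) is one month after the intervention ends.

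The same section describes a session as 30 minutes in which 20 minutes of stimulation run alongside gait training of rising difficulty. Sessions take place on weekdays over four consecutive weeks, and there is no control group. Only one test is tied to both sides of a session: "Before and after each session, individuals will be evaluated using the one-leg stand test". TUG and mDGI have no such pairing, and no rest period or minimum interval is set for them.

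**The concern.** The on-treatment values and the two values they are compared with may be taken in different states. After half an hour of demanding gait training with stimulation, a participant with ataxia may perform better than usual (immediate facilitation, warm-up) or worse (fatigue). At baseline and at one month neither applies. The repeated one-leg stand test shows that the Protocol allows for change within a session.

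Aim (ii) asks whether the extended course improves gait and postural control, and aim (iv) whether benefit is retained. If a single-session effect enters the session-20 value, facilitation would look like benefit followed by loss. Fatigue would hide a benefit and then look like a late gain. Timing is fixed when the data are collected. If only post-session values exist, no later analysis can remove the single-session part, and there is no control group to subtract it.

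**Working it through.** The Protocol gives no effect size, SD, alpha or power, so there is no stated figure to reproduce. The check has three parts.

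**1. What the timing text allows**

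- Outcomes 2 and 3 are tied to the end of named sessions, with the note that each session is one day. Outcomes 1 and 4 are timed more loosely, to completion of the course.
- Sessions run on consecutive weekdays. No session-free weekday lies between sessions 5 and 6, 10 and 11, or 15 and 16. Assessments 2 to 4 therefore fall on a session day or, where a block ends on a Friday, possibly on a weekend.
- Assessment 5 has no such constraint. It could follow session 20 directly or be held on a later day.

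**2. What each contrast contains**

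Score every effect so that positive means improvement. Let C be the cumulative effect after 20 sessions, C10 the cumulative effect after 10, R the effect retained at one month, and A the immediate effect of one session (positive for facilitation, negative for fatigue). On the literal reading:

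- baseline to session 20 = C + A
- session 20 to follow-up = R − (C + A) = R − C − A
- baseline to follow-up = R
- session 10 to session 20 = (C + A) − (C10 + A) = C − C10, if A is constant

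Examples in SD units of the change, with assumed values:

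| C | R | A | Baseline to session 20 | Session 20 to follow-up | Baseline to follow-up |
|---|---|---|---|---|---|
| 0.3 | 0.3 | 0 | 0.3 | 0.0 | 0.3 |
| 0.3 | 0.3 | +0.3 | 0.6 | −0.3 | 0.3 |
| 0.3 | 0.3 | −0.3 | 0.0 | +0.3 | 0.3 |
| 0 | 0 | +0.3 | 0.3 | −0.3 | 0.0 |

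If Assessments 2 to 4 follow a session but Assessment 5 is held on a separate day, A leaves the session-20 value but no longer cancels: session 10 to Assessment 5 = C − C10 − A.

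**3. Size, as illustration**

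Inputs: n = 45, the Protocol's upper limit. Assumed: a paired t test, two-sided alpha 0.05, C = 0, and A of 0.2, 0.3 or 0.4 SD of the change.

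- Standard error of the mean change = 1/√45 = 0.149 SD.
- Noncentrality = A × √45 = 1.34, 2.01 and 2.68.
- Probability of a significant baseline-to-session-20 change (noncentral t, 44 df) = 0.259, 0.503 and 0.747.
- With 30 participants the same shifts give 0.185, 0.355 and 0.563.

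For scale, the change detectable with 80% power at n = 45 is (1.960 + 0.842)/√45 = 0.42 SD.

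**The case against.** **Testing straight after a session is not stated.** A reader might infer that the Protocol prescribes it. It does not. The Abstract describes the interim assessments as occasions of their own. The exit interview is timed to the end of session 20 under Outcome Measures and to the end of the 20 sessions in section 3, so the phrase may mark a milestone rather than a clock time. This stands: post-session testing is the natural reading, not an explicit instruction. It does not remove the point, because the time frame as written permits post-session testing and nothing keeps the condition the same across visits or participants.

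**Aims (ii) and (iv) are not lost.** A reader might infer that neither can be answered. Baseline versus follow-up compares two session-free states, and aim (iv) names no reference visit. The part of aim (ii) about going beyond 5 to 10 sessions can use session 10 versus session 20, where a constant immediate effect cancels. This also stands.

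**The percentages are not false-positive rates.** The shifts are assumed, and the Protocol gives nothing to anchor them. An immediate response would itself be an effect of the intervention. The figures show how readily such a response could be read as a cumulative benefit.

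**Pre-session testing can bring in unequal gaps.** If the course starts on a Monday, tests before sessions 6, 11 and 16 follow a weekend, while a test before session 20 follows a single day. This is right, and the fix below avoids that combination.

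**Conclusion.** The point holds for two contrasts on two primary outcomes. Read literally, the baseline-to-session-20 and session-20-to-follow-up changes in TUG and mDGI may each carry a single-session effect, with opposite signs. Its direction and size are unknown. If it were 0.2 to 0.4 SD of the change, it could by itself produce a significant baseline-to-session-20 result in roughly a quarter to three quarters of trials of 45. That range rests on assumed shifts, no cumulative effect and a two-sided 0.05 paired test.

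Baseline versus follow-up is unaffected, and contrasts between on-treatment visits are unaffected as long as the immediate effect is constant and all those visits share one condition. The plan should be changed because the problem lies in a stated timing rule that analysis cannot repair and that costs little to correct.

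**What to change.** - Take TUG and mDGI before that day's stimulation and exercise, with the same gap since the last session at each on-treatment visit. Testing immediately before sessions 5, 10, 15 and 20 does this at visits that already take place. These sessions are five weekdays apart, so barring holidays they fall on the same weekday for a given participant and the gap is constant.
- If Assessment 5 is already held on a separate day after session 20, take TUG and mDGI there before any exercise, and keep and record the gap.
- Change the time frames of outcomes 2 and 3, and the matching sentences in section 3 and the Abstract, so that all state this condition.
- Report any post-session TUG or mDGI separately, as immediate effects.
- Name baseline versus follow-up as the retention contrast.

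Cost: rewording and a change of order within existing visits. Pre-session values reflect one session fewer (4, 9, 14 and 19 completed), so the last one describes 19 sessions rather than 20. Moving Assessment 5 to another day avoids that at the price of one extra attendance, which matters because section 3 notes participants' limited transport. An immediate effect that outlasts the gap would still be included.
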